including seizure frequency, seizure type, seizure onset, medication history, family history of seizure, and also developmental stages, will be recorded from electronic medical record. Besides, the CT-scan or MRI are also collected from the same source. After that, their quality of life will be assessed by QOLCE-55 validated questionnaire through self-guided report. Furthermore, the laboratory investigation and EEG will be performed.

The next phase is intervention phase, started from initial step and ended by the maintenance of new combination therapy, which takes with overall 12 weeks. Initially, the substitution drugs with each initial dose are consumed. The drugs consist of valproic acid for the generalized and carbamazepine for focal epilepsies. On the other hand, the control group will take lamotrigine or clobazam for generalized and oxcarbazepine for focal ones. The phase continuous to titration dose, in which, the dose is raised gradually until it causes 50% of seizure reduction, and the next step is maintained the dose for about 2 weeks.

The following is tapering-off and after that stopping the substituted drug, levetiracetam or topiramate, which is determined by considering individual condition. Yet, if the seizures increase more than one and a half time of the previous frequency during the phases, the intervention will be ended immediately. On the contrary, if the condition is better, then the children go to the maintenance of new combination, that is the substitution drug and the old drugs in which the seizures do not go up or even better keep going down. The children who complete all of the phases are categorized as responder. In case if the intervention is ended, the subjects will be given the former combination therapy with adjusted doses in order to decrease the seizures until reaching the pre-intervention condition. The subjects are categorized as non-responder, and will be dropped-out. The other criteria of drop-out are resignation, non-compliance of study procedure, and death in term of other causal not related to the study. While in term of lost to follow-up, is intended for those who do not attend the study without any possible reasons.

[figure not shown]

Figure 2. flow-chart of the study

Maintenance the dose of the new combination therapy that consist of the new drug and

Maintenance

old drug after stopping the substituted drug

Inclusion criteria

- 1. Children age at 1 18 years old

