- current anticonvulsant(s) with doses and formulation and its side effect (if presents)
- other medications and its side effect (if presents)

- first recognized seizure date
- prior EEG and laboratory which has been performed at the baseline phase
- physical examination

Follow-up data

Follow-up data will be collected during regularly scheduled clinic visits (per 2 weeks). This information will be obtained from the participants' diary card. Important information to be collected at follow-up will include:

- physical examination
- adverse drug reaction of the substitution therapy that happen
- seizure's frequency
- type of seizure
- complaint

Outcome evaluation

- a. The difference in responders was the difference in the percentage of responders in the group that used first line OAE again as substitution therapy and those that used standard therapy. Responders are subjects who experience a decrease frequency of seizure more than or equal to 50% of the initial seizure. Frequency of seizure is the number of seizures that occur within 1 month. In previous studies, it was said that the frequency of seizures was said to have decreased significantly or was said to respond if the seizures were reduced by 50% or more from the initial seizure. ^{19, 29} Based on this, researchers will categorize the frequency of seizures into:
 - Responder: there is a decrease in the frequency of seizures by 50% or more than before
 - Non-responder: namely the frequency of seizures remains or decreases but not up to 50% of the initial seizure frequency or the frequency is more than before

Furthermore, the proportion in the form of the percentage of respondents in the two groups is calculated and differentiated, therefore it is classified into two groups:

- Different : when a significant difference is shown in difference of proportion test of the 2 unpaired groups.
- Not different: when there is no significant difference is shown in difference of proportion test of the 2 unpaired groups.

- b. Differences in quality of life: quality of life assessment using QOLCE-55 instrument. The average of each function (cognitive, emotional, social and physical functions) and the average of the total functions are assessed. This variable is categorized into:
 - Different, if there is a difference in the average quality of life
 - Not different, if there is no difference in the average quality of life
- c. Differences in electroencephalography appearance

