P1 proportion of reduced seizure on the new drug (the proportion of reduced seizure on the standard drug in addition to the minimal difference that is considered significant)= 0.7 + 0.25 = 0.95

Q1
$$1 - P1 = 1 - 0.95 = 0.5$$

P
$$(P1 + P2) / 2 = (0.95 + 0.7) / 2 = 0.825$$

Q
$$1-P = 1-0.825 = 0.175$$

In this study, it was found that the proportion of seizure reduction on standard drugs was 70%.³⁰ Therefore the equation:

$$n1 = n2 = \left(\frac{1,96\sqrt{2(0,825)(0,175)} + 0,84\sqrt{(0,95)(0,5) + (0,7)(0,3)}}{0,25}\right)^2 = 49,56 = 50$$

$$n\ 2\ groups=100$$

Based on the formula above, 100 research subjects are required. An additional of 10% from the total number of subjects are needed as there is a possibility of those dropping out, therefore a total of 110 subjects are needed in this study.

Statistical Analysis

- 1. Analysis of differences in the proportion of responders (primary outcome), differences in EEG appearance (secondary outcome) in pediatric epilepsy patients who are resistant to the combination of second line OAE between those who reused first line OAE as substitution therapy and those who used standard therapy. Data type is categorical. Data is analyzed the Chi-square statistical test, if it does not meet the requirements then an alternative test is performed, known as Fisher's multiple test. The significance level (α) is 5% and the research confidence level is 80%. If p value ≤ α is obtained, this means H0 is rejected, which means that there is a difference seen in seizure frequency between reusing first line OAE as substitution therapy and standard therapy.
- 2. Analysis of differences in the mean quality of life with an unpaired T test if the data distribution is normal or Mann-Whitney if data distribution is not normal
- 3. To assess drug effectiveness, the analysis used was the difference in actual failure between those using first line OAE as substitution therapy and those using standard therapy (primary outcome). Formula:

$$ARR = CER - EER$$

CER: the incidence of increased seizure frequency in the standard therapy group ERR: the incidence of increased seizure frequency in the group in substitution therapy with 1st line OAE The increase in seizure frequency in this study shows therapy

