This test will use 2 analyses known as intention to treat analysis and per-protocol analysis. Intention to treat analysis means that all research subjects who have been randomized are included in the analysis according to their initial allocation regardless of whether or not the subject is taking the drug/therapy being tested or a placebo, or whether these subjects died before taking the drug being tested. Subjects who did not

failure.

take medication, lost to follow-up, and who moved to another group, are considered failures of their original group.

Whereas per protocol analysis only includes subjects who complete the research to the end.

- 4. Analysis of the difference in time to achieve a decrease in seizure frequency with the chisquare test or if it does not meet the requirements, an alternative test is performed, namely the Mann-Whitney test
- 5. Analysis of clinical characteristics, side effects of OAE, and laboratory findings of complete blood count (hemoglobin, hematocrit, leukocytes, platelets, and type count), liver function (SGOT and SGPT), kidney function (urea and creatinine), and blood electrolytes (sodium, potassium, calcium, chloride) in pediatric epilepsy patients who are resistant to combination second OAE who re-use first line OAE as substitution therapy and who use standard therapy (secondary outcome). All existing data is processed and presented in a table consisting of mean and standard deviation or median and inter-quartile range, as well as frequency distribution.
- 6. Analyzing factors that affect the decrease in the frequency of late seizures (age, seizure onset, seizure type, family history of seizures, developmental delays, history of OAE, initial seizure frequency, initial EEG, brain structural abnormalities) in pediatric patients with resistant epilepsy combination of second line OAE who re-use first line OAE as substitution therapy (secondary outcome).

Data is categorical. Data is analyzed using Chi-square statistical test, if results do not meet the requirements then an alternative test will be performed, known as Fisher's multivariate test and further analyzed with multivariate test and logistic regression analysis. The significance level (α) is 5% and the research confidence level is 80%. Results will show statistically related if value of $p \le \alpha$ is obtained.

Ethics and dissemination

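### The per-protocol set drops children because their seizures worsened, and the plan does not make intention-to-treat the primary analysis of responders

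*Combined protocol and SAP*

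**What the plan says.** **Study procedure.** The stopping rule is tied to the outcome: "if the seizures increase more than one and a half time of the previous frequency during the phases, the intervention will be ended immediately". For children who are stopped, the text says: "The subjects are categorized as non-responder, and will be dropped-out". On the others: "The children who complete all of the phases are categorized as responder".

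**Outcome evaluation, a.** The definition here is different: "Responders are subjects who experience a decrease frequency of seizure more than or equal to 50% of the initial seizure".

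**Statistical Analysis, item 1.** This is the responder comparison: "Analysis of differences in the proportion of responders (primary outcome". It uses a chi-square test, and "if it does not meet the requirements then an alternative test is performed, known as Fisher's multiple test". No analysis set is named.

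**Statistical Analysis, item 3.** This is the difference in failure, ARR = CER − EER, where failure is increased seizure frequency. It is also labelled primary. The paragraph after the formula refers back to a single test and names two analyses. Intention-to-treat takes every randomised child by allocation and counts untreated, lost and switched children as failures. Per-protocol is limited in this way: "Whereas per protocol analysis only includes subjects who complete the research to the end". Intention-to-treat is mentioned first. No sentence makes it decisive or says what happens if the two analyses disagree.

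**The concern.** A child stopped for worsening seizures is a treatment failure. The plan labels that child a drop-out as well, and a set restricted to completers then leaves the child out. Membership of the per-protocol set therefore depends on the outcome being compared. The arm in which more children worsen loses more failures and can look better for it.

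A completers-only set does little harm as a stated supportive analysis, but nothing in the plan makes it supportive. Item 1 could be run on all randomised children or on completers. The trial is open-label, so neither stopping nor the later choice of set is protected by blinding. At stake is the main efficacy conclusion: a false difference between equal arms, or a real difference partly hidden.

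**Working it through.** **The plan's own figure.** Sample size uses P1 = 0.95, P2 = 0.70, Z = 1.96 and 0.84, and states 49.56, rounded to 50 per group. With the printed Q1 = 0.5 the formula gives 48.91, so 49, which is close to the stated value. Since 1 − 0.95 = 0.05, the correct Q1 gives 35.02, so 36. That slip is a separate matter, but it explains why power at 50 per arm is well above 80% before anyone is dropped.

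**The two responder rules side by side.** Read literally, Study procedure makes every completer a responder. The per-protocol set is then 100% responders in both arms and no test is possible. Under Outcome evaluation a, children with less than a 50% reduction can complete, so only part of the non-responders is lost. The scenarios below use this second rule.

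**Assumptions.** The dropped shares are assumed. Tests are two-sided at 5%. The plan gives no threshold for switching tests, so Fisher's exact test is used when any expected count is below 5, and the uncorrected chi-square otherwise. Rejection rates are exact, summed over all possible numbers of completers and responders.

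**(1) Planning rates, same share f of non-responders dropped in both arms.** Completer rate = p / (1 − f(1 − p)). For f = 0.5: 0.95/0.975 = 0.974 and 0.70/0.85 = 0.824.

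| f | Completer rates | Difference (points) | Power, 50 per arm | Power, 55 per arm |
|---|---|---|---|---|
| 0 | 0.950 vs 0.700 | 25.0 | 94.7% | 96.0% |
| 0.25 | 0.962 vs 0.757 | 20.5 | 86.5% | 89.8% |
| 0.50 | 0.974 vs 0.824 | 15.1 | 68.2% | 73.3% |
| 0.75 | 0.987 vs 0.903 | 8.4 | 33.7% | 38.5% |

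A normal-approximation check at 50 per arm gives 92, 84, 68 and 43%, the same pattern. The shrinkage depends on the rates: at 45% vs 20% with f = 0.5, the completer rates are 0.621 and 0.333, and the difference grows from 25 to 28.7 points.

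**(2) Equal true responder rates of 70%, unequal stopping.** If a share s of all children is stopped, completer rate = 0.70 / (1 − s). Controls have s = 0.05, so 0.737.

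| Intervention s | Completer rate | False difference (points) | False positives, 50 per arm | 55 per arm |
|---|---|---|---|---|
| 0.10 | 0.778 | 4.1 | 7.5% | 7.7% |
| 0.15 | 0.824 | 8.7 | 16.5% | 17.6% |
| 0.20 | 0.875 | 13.8 | 36.6% | 39.5% |

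With all randomised children analysed, the rate is 5.0% at 50 per arm and 5.1% at 55.

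**(3) Item 3, with 20% stopped in the intervention arm and 5% in controls.** Intention-to-treat ARR = 0.05 − 0.20 = −15 points. Per-protocol can count only increases that did not exceed the trigger. With none, ARR = 0. With 5% of each arm having a smaller increase, ARR = 0.05/0.95 − 0.05/0.80 = 0.0526 − 0.0625 = −1.0 point, while intention-to-treat stays at −15.

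**The case against.** The plan already holds most of the protection. It names intention-to-treat, keeps all randomised children by allocation, counts lost and switched children as failures, and labels stopped children non-responders. An intention-to-treat result is promised for item 3. The text at the end of item 3 is also disordered in the extracted document, so the paragraph on the two sets might have been meant for both primary analyses. This is fair, and a valid analysis can be assembled from the text. But even if the paragraph covers item 1, neither set is ranked.

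The larger scenarios go beyond the plan's drop-out allowance. Ten extra among 110 is 9.1%. Dropping 75% of non-responders means 3.75% and 22.5% of the arms, an average of 13.1%; stopping 20% vs 5% averages 12.5%, and 15% vs 5% averages 10%. Within the allowance lie f = 0.25 (average 4.4%), f = 0.50 (8.75%) and 10% vs 5% stopped (7.5%). This stands as a caution on size. An allowance is not a cap, however, and it must also cover withdrawal and loss to follow-up.

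Many non-responders have unchanged or modestly reduced seizures and would not trigger the stopping rule, and the direction of bias varies with the rates. Both points are right. They limit what can be said about size, but the set is still selected on outcome.

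**Conclusion.** The concern holds and should be fixed. The drop-out rule and the completers-only rule together exclude failures by outcome, and the plan does not commit to the valid analysis it describes.

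Within the drop-out allowance, the illustrations give power of 86.5% to 68.2% instead of 94.7% at the planning rates, and a false-positive rate of 7.5% instead of 5.0% for 10% vs 5% stopped. Beyond it, they reach 33.7% power and 36.6% false positives. These figures rest on assumed stopping shares, on the 50%-reduction definition, on the assumed rule for switching to Fisher's test, and on item 1 being run on completers. The text permits that last choice but does not state it. On the literal Study procedure labels, a completers comparison of responders carries no information at all.

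**What to change.** - State intention-to-treat by allocation as the primary analysis for items 1 and 3.
- Count stopped, withdrawn and missing children as non-responders in item 1 and as failures in item 3.
- Label per-protocol supportive and define it by eligibility and compliance. Keep children stopped for increased seizures in it as failures.
- For analysis purposes, separate ending the intervention from leaving the study.
- Reconcile the responder definitions in Study procedure and Outcome evaluation a.

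The stopping rule itself is not touched. The cost is protocol and SAP wording, with no extra visits or data. Counting missing children as failures is conservative and may lower the reported responder rates slightly. If missingness differs between arms it can also shift the difference, so numbers and reasons should be reported by arm.

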Randomized studies in drug-resistant epilepsy typically involve addition of new anti-epileptic drugs. However, in clinical practice, if the patient is already taking multiple drugs, then substitution of one of the current medications commonly occurs, despite little evidence supporting this approach.²² The choice of the substitution drug depends on the mechanism of action, the pharmacokinetic profile, drug-drug interaction, and the risk of seizure exacerbation as well as patients-related factors. The new combination is intended to maximize efficacy and minimize toxicity. However, the availability and cost-effectiveness should also be

taken into consideration since the patient would not reach the goal of ideal combination of drugs if they could not afford it nor even get the medication. ²³⁻²⁶ Another considerable case is one of drug resistance patterns in which at the first-time patients may not responsive to treatment yet they change into a state that is responsive to the medication. ²⁷ The choice of substitution therapy may originate from firs-line AEDs since evidences have shown they have equal efficacy to those of second-line ones. However, there is still lack of evidence whether the drug resistance pattern occur if the substitution drug is originated from first-line AED even more if it has ever been given prior to the current drug combination. ²⁷ The study aims to analyzed the efficacy and safety of first-line AEDs as substitution therapy in drug-resistant epilepsy children.

Primary Objective

The primary outcome of the research is to analyze the proportion of responders, who are defined as subjects who get 50% of seizure reduction.

Secondary Objectives

There are some secondary objectives of the study. The first one is to analyze the differences of improvement of quality of life, EEG feature and time to achieve seizure reduction, between the intervention and the control group. Besides, the research will describe the clinical characteristics, adverse effects of the drugs and laboratory features related to the adverse effects, among children with drug-resistant epilepsy. Furthermore, it will explain factors influencing the reduction of seizure frequency

Study Design

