This protocol is intended for a multicenter open label experimental, randomized controlled trial on the efficacy and safety of using first line AEDs as substitution therapy in childhood drug-resistant epilepsy. It will prospectively follow 100 children up during 14 weeks that consist of baseline, intervention, and post-intervention phases. While the intervention consists of 6 steps, as described at the Figure 1 below.

[figure not shown]

Figure 1. Timeline of the intervention phases

The study will be conducted at pediatric outpatient clinic of 3 referral hospitals in Jakarta, Cipto Mangunkusumo Hospital, Harapan Kita Hospital and Fatmawati Hospital. Children who are diagnosed with drug-resistant epilepsy receiving levetiracetam or topiramate will be enrolled in the study. Enrollment begins as soon as the research ethics committee approval is obtained from The Ethics Committee of The Faculty of Medicine, University of Indonesia-Cipto Mangunkusumo Hospital. The study will be closed after the last recruited patient has been followed up for the required 14 weeks.

All recruited children will be examined for monitoring at the hospital where the intervention is initiated. To avoid selection bias, all patients who met the inclusion criteria are divided into two groups, the intervention and control groups. Prospective participants and their parents will be provided with information related to the study. Patients will then fill out an information sheet containing demographic data, comorbidities, developmental history, school history, history of drug consumption, as well as history of seizures and patient complaints. All the data will be extracted and recorded on the case report form. Patients and their parents should be informed that participation is voluntary and they are free to withdraw from the study at any time. They should also be informed that refusal to participate or withdraw from the study will not affect the quality of treatment received. In the event of their withdrawal, it will be explained that the data collected so far is irrevocable, and we will seek consent to use such data in the final analysis if necessary.

Study procedure

Study procedures are depicted in Figure 2. The patients who are eligible for the study and have given their consents, will be enrolled, divided into 2 groups, the intervention and control, then start the 3-day baseline phase. In this phase, data such as demographic, clinical characteristic

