- 2. Children diagnosed as drug-resistant epilepsy by pediatric neurologists, diagnosis was based on the ILAE 2017 criteria
- 3. Children will have got at least 3 months of combination therapy that consists of levetiracetam of topiramate with optimal of therapeutic dosages

Exclusion criteria

- 1. Non-convulsive epilepsy
- 2. Suffered from status epilepticus in the prior 3 months before the study begins
- 3. Past medical history of idiosyncrasies or severe adverse drug reactions caused by the substitution therapy that will be given

Instrument of the study

QOLCE-55 questionnaire

Once the children are enrolled, quality of life will be assessed by using validated QOLCE-55 questionnaire. It is parent-reported and self-administered questionnaire which assess quality of life children with epilepsy age 4-18 years of age. The researcher will give a detail explanation about filling the questionnaire. It has 55 questions including cognitive (22 items), emotional (17 items), social (7 items) and also physical (9 items) function. Items are rated on a five-point Likert scale, 0 = very often, 1 = fairly often, 2 = sometime, 3 = almost never, 5 = never. The composite score is the unweighted average of the four subscales, ranging from 1-100, higher score indicates better quality of life.²⁸

Diary Card

The other important thing to evaluate is subjects' adherence, seizure frequencies, and adverse drug reaction by self-reported diary card which is filled by the parents each day during the intervention phase. Besides, drug consumption compliance is also assessed by counting the tablets or powder packages during routine visits of the study.

Electronic Medical Record

Electronic Medical Record is used to collect secondary data that include demographic data, clinical characteristic, and imaging such as brain-CT or brain-MRI.

Laboratory Examination

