The test is performed in hospitals' laboratory where the study take place and is done twice, at the baseline and post intervention phase. The order of the blood test consists of complete blood test, liver function test including alanine and aspartate transaminase, kidney function test including urea and creatinine, and also blood electrolyte that consist of natrium, kalium and calcium. The laboratory professional takes the blood from vein of the arm. The subjects are seated or lying down, accompanied by the parents, while for the younger children, they seat on his/her parents' lap or position that make them feel comfortable. Older children may be asked to make a fist and then will be tied by a rubber band around his/her arms. After that, the needle is inserted the needle until the blood is drawn. The laboratory worker will take the needle since the amount of blood is enough and puts an adhesive bandage over the site. The next step is analyzes of the sample and the result will be issued for about 1-2 days both printed or provided on the electronic medical record.

Electroencephalography Examination

The EEG examination is operated two times, at the baseline and post intervention phase, with high density machine (Caldwell Easy III) is done twice, pre- and post-intervention. The machine will operate for about 45 minutes including 5 minutes each for eye-open and eye-close in every subjects. Beginning with acquisition, EEG recordings use standard parameter to analyze brain activity at various frequencies to gain good quality and artefact-free result. The printed results of the EEG is available for about 4-7 days after the examination.

Data collection

All relevant data will be recorded, by nominated member(s) of the research team, on a case report form (CRF). Each participant will have a CRF and be assigned a unique identification number.

Baseline data

At entry into the study, the following baseline information will be recorded in the CRF:

- unique patient identification number contact telephone number and/or email address
- date of entry into the study
- eligibility for study entry based on inclusion/exclusion criteria
- age at study entry, in years and months
- gender
- weight and height
- seizure type (eg, generalized tonic clonic, absence, myoclonic and partial)
- the age at diagnosis and duration of epilepsy
- seizure frequency or average number of seizures per month

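### Item 4 compares time to seizure reduction with no event, no clock and no rule for children who never reach it, are stopped or leave; one fully specified time-to-event analysis should replace it

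*Combined protocol and SAP*

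**What the plan says.** Secondary Objectives lists, among the outcomes to be compared between arms, "EEG feature and time to achieve seizure reduction". The only analysis text for it is Statistical Analysis, item 4: "Analysis of the difference in time to achieve a decrease in seizure frequency with the chisquare test". Mann-Whitney is the fallback when requirements that are not named are not met. Outcome evaluation (a to e) has no entry for this endpoint. It defines a responder by a fall of at least half, and seizure frequency as a count over one month. Item 4 speaks only of a decrease, with no size.

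The route through the trial matters here. Under Study procedure, children are "divided into 2 groups, the intervention and control, then start the 3-day baseline phase". In titration "the dose is raised gradually until it causes 50% of seizure reduction"; a maintenance step and then tapering follow. If seizures rise beyond a stated limit, the intervention ends: "The subjects are categorized as non-responder, and will be dropped-out". Discontinuation of study participation also lets the investigator withdraw a child who does not stay in the study as far as tapering.

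On data, the diary is "filled by the parents each day during the intervention phase". Baseline data on the CRF include "seizure frequency or average number of seizures per month". Visits are two-weekly. Item 3 has a rule that counts as failures the children who take no medication, are lost, or change group, but it is written for item 3's own comparison.

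**The concern.** A time comparison needs a time, a rank or a censoring rule for every child. Neither named test supplies one. Chi-square on reached versus not reached ignores time and largely repeats the responder test in item 1. Mann-Whitney needs a rank for everyone, and if only children with a time are used, it conditions on the outcome. The two tests answer different questions, so one is not a like-for-like fallback for the other, and the trigger for switching is not stated.

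Responder status does not fill the gap. Tapering comes after the 50% point, so a child stopped for worsening during tapering may already have a genuine event time although labelled a non-responder. At stake is a secondary result in an open-label trial that could change with choices made after the data are seen.

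**Working it through.** **1. The plan's own figure.** No size or power is given for the time endpoint. The stated calculation is for the responder proportion. The printed inputs give ((1.96√(2×0.825×0.175) + 0.84√(0.95×0.5 + 0.7×0.3))/0.25)² = 48.9, close to the printed 49.56. (Q1 is printed as 0.5, whereas 1 − 0.95 = 0.05. That is a separate matter.) Only the example rates, 70% and 95%, and 50 children per arm are carried forward.

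**2. Children without a time.** Control: 50 × (1 − 0.70) = 15. Intervention: 50 × (1 − 0.95) = 2.5. These are upper figures for non-response, because some non-responders meet a diary criterion by chance. With a single-visit 28-day event at 4 seizures a month, about 86% of controls meet it, so about 50 × 0.14 = 7 lack a time.

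**3. Readings that fit item 4.**
- Chi-square on reached/not reached.
- Chi-square on grouped times with a not-reached category, which keeps time; but no grouping is given.
- Mann-Whitney in reachers only.
- Mann-Whitney on all children with never-reached ranked last, which is workable; but the rule is not stated.

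**4. How far the choice matters.** Simulated power, 50 per arm, two-sided 0.05, 95% versus 70%:

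| Event | Log-rank, all | Mann-Whitney, never-reached last | Mann-Whitney, reachers only |
|---|---|---|---|
| Exact exponential times | 0.99 | 0.97 | 0.51 |
| Same timing among reachers, 10% leaving | 0.79 | 0.54 | 0.05 |
| 28-day diary, one visit, 4 a month | 0.48–0.60 | 0.36–0.48 | 0.13–0.21 |
| Same, 8 a month | 0.77–0.86 | 0.68–0.78 | 0.18–0.26 |
| Same, 20 a month | 0.94–0.97 | 0.91–0.95 | 0.22–0.32 |

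Diary rows assume Poisson counts, a known baseline, exponential onset of response and a 60% or 75% fall after onset (the two ends of each range). As a check on the first row: hazard ratio = ln 0.05 / ln 0.30 = 2.49, and expected events = 47.5 + 35 = 82.5. The Schoenfeld approximation gives Φ(ln 2.49 × √(82.5/4) − 1.96) = Φ(2.18) = 0.985. At 85% versus 70%, log-rank power for the diary event is only 0.15–0.17, 0.25–0.29 and 0.40–0.45 at 4, 8 and 20 a month.

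**5. Children who leave.** These are false-positive rates with no true difference, using the single-visit diary event.
- Drop-out unrelated to response, 5% versus 15%: log-rank 0.05, last-rank Mann-Whitney 0.06–0.07, chi-square 0.07–0.10.
- The same at 0% versus 20% (extreme): 0.05, 0.10–0.11 and 0.14–0.24.
- Withdrawal because the child has not responded, one arm only (extreme), treated as censoring: log-rank 0.08, 0.12 and 0.22 at 4, 8 and 20 a month; last-rank 0.05–0.06.

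If such children are withdrawn in both arms and censored, log-rank power at 95% versus 70% (70% fall) drops from 0.58, 0.85 and 0.96 to 0.43, 0.69 and 0.85. Last-rank Mann-Whitney gives 0.47, 0.79 and 0.93. The investigator-withdrawal rule can produce this pattern, because tapering follows the 50% point.

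**6. Chance events.** In a child with no true change and a Poisson mean of 4 per 28 days, one window shows 2 or fewer with probability 0.24. The three non-overlapping windows in 12 weeks alone give 1 − 0.76³ = 0.56. With all five visits (weeks 4 to 12), simulation gives 65%, 35% and 5% at 4, 8 and 20 a month. Requiring two consecutive visits cuts this to 30%, 10% and 0.5%. Log-rank power at 95% versus 70% is then 0.58–0.78, 0.78–0.91 and 0.87–0.96.

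**The case against.** The item 3 failure rule stands next to item 4 and could be borrowed. It does not close the gap: it gives a status, not a time, and item 4 does not invoke it.

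Item 4 says time, so its chi-square may be meant for grouped times. That is fair. The valid complaint is that no grouping is stated, not that chi-square must discard time.

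The choice of log-rank is partly preference. This stands too. If 70% respond in both arms and only timing differs (2–8 versus 2–12 weeks), exact-time power is 0.21 for log-rank, 0.41 for last-rank and 0.83 for reachers-only Mann-Whitney. For the diary event, log-rank and last-rank are close (0.12–0.51 and 0.09–0.53). Log-rank's protection against false positives holds only when drop-out is unrelated to response; step 5 shows that it fails otherwise.

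A reader might therefore infer that log-rank is generally the stronger test, or that any pre-stated Mann-Whitney is wrong. The documents and the calculations support neither.

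**Conclusion.** The gap is real and should be closed; confidence in that is high and does not rest on any simulation. Item 4 names two tests but no event, clock, time grouping, analysis set or handling of children without a time. At the plan's example rates this touches up to about 15 of 50 controls and 2–3 of 50 intervention children through non-response, and the exact number depends on the event definition. Where the arms differ in who responds, using reachers only loses much of the power: in step 4 it falls to about half or less of the log-rank value.

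Confidence in those sizes is moderate. The rates are the plan's illustrative values. Seizure frequency, size of fall, timing and drop-out are assumptions, and overdispersed counts and error in the recorded baseline are not modelled.

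A reader might infer that the trial's main conclusion or its size is at risk. It is not: this is a secondary endpoint, and neither the responder test nor the sample size uses item 4.

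**What to change.** Replace item 4 with Kaplan-Meier curves and one pre-stated log-rank test on grouped visit times, by allocated arm, specifying:

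- **Clock:** the first day of the intervention phase, when the diary begins. Counting from allocation would leave only 28 − 3 = 25 diary days at week 4.
- **Event:** past 28-day diary count at least 50% below the CRF monthly baseline (scaled to 28 days) at two consecutive two-weekly visits from week 4, dated at the second. It is for analysis only and does not alter the 50% point used in titration.
- **Reached, then worsened:** keep the event time.
- **Not reached, and stopped for worsening or withdrawn by the investigator for not getting as far as tapering:** keep in the risk set as not reached to week 12.
- **Lost or withdrawn for reasons unrelated to response:** censor at the last diary date. State that children lost before the first possible event date (week 6) add no information.
- **Sensitivity analysis:** treat all lost or withdrawn children as never reaching the event, in line with item 3.

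Mann-Whitney on all randomised children with never-reached ranked last is an acceptable alternative if the rule is stated in advance.

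The cost is SAP wording and one derived variable, fixed before outcome data are examined. No new visits or data are needed. There are three downsides. Diary event dates lag the true response: by a median of 3–4 weeks in simulation with the single-visit event, and the two-visit rule dates the event at a later visit. The baseline comes from the CRF, not the diary. At 20 seizures a month the two-visit rule gives up a little power (0.87–0.96 against 0.94–0.97).
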